4. SUMMARY

Reducing unintended pregnancy is a national and global priority, and improving women's choice of contraception is a vital step. There are many myths, misunderstandings and concerns about contraception, and increasingly women turn to online resources for information on healthcare.

The aim of the study is to develop and test the feasibility of an online trial of a website to increase the acceptability, uptake and adherence to long-acting reversible contraceptive (LARC) methods in young women. LARC methods include the intrauterine device (IUD), intrauterine system (IUS), subdermal implant (SDI) and depo injection.

In Phase 1 of this study (completed) we developed a self-guided website that presents recommended contraceptive options in response to women's preferences. The website will be presented on a touch-screen tablet computer in clinic waiting areas or pharmacy consulting areas.

In Phase 2 (this study), we will assess feasibility of an online trial of the contraception choice website in five sites:

An NHS sexual health service (Margaret Pyke Centre, MPC)

A local general practice

A maternity service (Ashford & St Peter's Hospitals NHS Foundation Trust)

A community pharmacy (Greenlight)

An abortion service (bpas)

Phase Two will take 15 months including:

- Conducting a randomised pilot trial across the five settings
- Conducting a qualitative process evaluation of the website, of NHS implementation issues and of research procedures
- Analysis, reporting and dissemination of study findings
- Preparation of outputs, including a protocol for a definitive RCT to increase uptake and adherence of LARC that is informed by both quantitative and qualitative findings In each setting we will recruit 80 women aged 15-30 years (40 randomised to intervention and 40 to control) and follow them up by online questionnaire at 3 and 6 months (or 2 months after delivery for post-partum women).
- *Funder-approved amendment to recruitment*. In addition to the above, we will recruit 530 more women from one site only, the Margaret Pyke Centre, via their Central (telephone) Booking System. Women requesting an appointment for

contraception will be invited to go online and enter the trial before they attend their appointment.

Data collection:

All quantitative data will be collected online. Using methodology we developed and implemented for a the Men's Safer Sex pilot trial, eligibility will be checked with a few screening questions, then eligible women will be asked for informed consent, demographic information, baseline sexual health outcomes, an email address, mobile phone number and postal address. A computer algorithm will automatically assign participants randomly to intervention or control group. All participants will be offered vouchers (by email) worth £20 on completion of follow-up at 6 months.

Funder-approved Amendment to outcomes measures: (this effectively converts the previously secondary outcomes related to contraception into primary outcomes)

The main outcome measures are

- LARC method in use at 6 months
- Satisfaction with any chosen method of contraception at 6 months

Secondary Quantitative Outcomes

- Follow-up rate at 6 months
- Recruitment rate;
- Effectiveness of contraceptive method in use at 6 months
- Pregnancy by 6 months
- Sexually transmitted infection diagnosis by 6 months
- Health service and out-of-pocket costs for contraception and other sexual health services

We will assess the feasibility of collecting the relevant **cost and outcomes** for the website and contraceptive methods provision in each setting including costs to third sector organisations and any out of pocket costs to patients. We will also calculate the cost of the development of the website and number of potential future users to estimate the cost per patient of the website.

[figure not shown]
Qualitative Outcomes include

- women's views and experience of the intervention and trial procedures, specifically including socially disadvantaged young people
- provider views about trial procedures, the role of a web-based intervention for contraception, and implications for clinical services .

Assessment of trial feasibility:

Feasibility will be assessed and reported in terms of intervention acceptability and key process measures for a definitive RCT including: recruitment and follow-up rates and qualitative assessment of contextual factors, including comparative ease of implementation in different settings. Particular attention will be paid to aspects of feasibility relating to implementation in routine NHS practice and other clinical settings of a website for contraception choice that can be accessed by tablet computer and/or mobile phone.

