Long-acting reversible contraceptive (LARC) methods, including intrauterine devices, depo injection and subdermal implants, offer women the most effective protection against pregnancy. Women who use oral contraceptive pills, the contraceptive patch, or vaginal ring have a 20 times higher failure rate than women who use LARC methods (2). Nearly a decade ago, NICE concluded that increasing uptake of LARC is more cost-effective in reducing unintended pregnancy than the contraceptive pill or condoms even at one year (3). At that time estimated uptake of LARC in the UK was low at 8% (2003/4 data) compared with 25% for the pill and 23% for male condoms. Since then, uptake of LARC has increased, but only slowly to 12% in the population in 2008/9 and to 30% by 2013 in women attending community contraceptive clinics (4). Even in specialist community services, younger women are less likely to use LARC (24% in those under 30 years) than older women.

There are **multiple pathways** by which women get information about contraception and choose a method. The main sources of information are the internet, family and friends, school sex and relationships education (SRE), general practitioners, community pharmacies and sexual & reproductive health services. However, not all these sources provide information on LARC and uptake of LARC is limited by the number of appropriately trained

doctors or nurses to fit them: many general practices - where 75% to 80% of contraceptive consultations occur - have little or no capacity for fitting and therefore rely on referral to specialist contraceptive services. The emergency intrauterine device (IUD) is much more effective than the emergency pill, but uptake of the emergency IUD remains low and community pharmacies - the first destination for the majority of young women seeking emergency contraception - cannot provide the emergency IUD. Recent surveys show that women's knowledge and experience of post-natal contraception is often poor (Sex and contraception after childbirth. British Pregnancy Advisory Service July 2014). Effective interventions are needed that expand women's choice of more effective methods of contraception, and improve uptake in a variety of settings.

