10.1. Inclusion and exclusion criteria

Inclusion criteria:

Women aged 15 to 30 years with a need for current or future contraception, attending one of the study sites, able to read English, with an active email account and access to the internet.

Exclusion criteria:

Women unable to provide informed consent (e.g. severe learning difficulties). Women needing a language advocate to understand English since the intervention content is intended to be accessed in private.

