It is routine practice at the Margaret Pyke Centre to send patients a text message to confirm their appointment. For this study, women who have booked a contraceptive appointment will be sent an additional text informing them that the clinic is taking part in a study to improve information about contraception, and inviting them to go online (by clicking on a hyperlink) and see if they want to take part in the study before they attend their appointment. Clicking on the hyperlink will take women to the trial website from where all procedures are the same as above.

Randomisation procedures

A randomisation list will be generated for the trial by a random number based algorithm in the computer software Stata. This list will be incorporated into the trial software programme before the trial begins, to allocate all participants to either the intervention or control condition. This allocation will be unalterable. Allocation will be concealed until the point of allocation, which will be immediate.

Participants allocated to the control condition will be notified that they have not been selected to view the intervention and told they will be contacted again in 3 and 6 months (or two months post-partum) to gather follow-up data. Those allocated to the intervention condition will be directed to the intervention website. Patients may stop viewing the website whenever they wish, and buttons will be included on the web pages to exit, recording whether they exiting because they want to (e.g., if they're bored), or if they are being called in to see the clinic staff. This data will be recorded, in order to give information about feasibility of website usage in practice.

For patients recruited through the MPC Central Booking Office there will be a variable interval of a few days before they attend their clinic appointment. All other registration and

intervention viewing is designed to take place in the waiting room, whilst patients are waiting to be seen by the clinic staff. This is designed to mimic how the intervention may work in practice – it can be offered to patients on arrival, so that they can complete activities in the time that they are waiting (often up to an hour).

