10.4. Questionnaire Measures

Demographics:

Participants will be asked to complete a demographic questionnaire at baseline, which will assess relationship status, age, employment status, and ethnicity (See Demographic questionnaire).

Contraception questionnaire:

Participants will be asked to complete a questionnaire at baseline, and at 3 and 6 month follow-up to assess what contraceptive methods, if any, they are using currently or have used before (baseline) or since enrolling in the study (at follow-up). Participants who are currently using contraception will be asked how satisfied they are with the method. At follow-up only, participants will be asked if they have had a pregnancy and, if they have, the outcome of the pregnancy (ongoing, gave birth, miscarried, terminated, or prefer not to say). All participants are asked at baseline, 3 and 6 months, whether they have been told by a doctor or other health professional that they have a sexually transmitted infection.

Service use related to contraception and sexual health:

Participants will be asked to specify where they go to get their contraception and if they pay for it themselves.

Interaction with the intervention

In order to assess engagement with the intervention (and whether this is related to outcome), we will record website usage. The software used will record the number of times

each user visits the site, the amount of time spent on the site, the pages visited, and the amount of time spent on each page.

Methods to protect against sources of bias

Participants will provide baseline data on the tablet device before randomisation. Once eligibility for the study is established, and baseline data are collected, allocation to intervention or control group will be determined from the randomisation list, and this will not be changeable by participants or researchers. Subsequent outcome data will be collected online using an emailed weblink to the online outcome questionnaire. Data will be saved on an encrypted server, and data exported will be identifiable by study ID numbers only. Most data collection procedures are therefore automatically blind to allocation to intervention or control group, since they are automated. Sealed envelope will grant access to group allocation only to those who need to know, to for data analysis.

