The primary outcome of LARC use at 6 months will be analysed among women in need of contraception (not pregnant or currently trying to become pregnant) and the primary outcome of satisfaction with method will be analysed among women who are using a method at 6 months. The primary outcome of LARC use at 6 months will be analysed stratified by LARC use at baseline, leading to three intervention effects: the effect in baseline LARC users, the effect in baseline non-users, and the overall effect adjusted for baseline LARC use. In the event that over 90% of baseline LARC users in the control arm are using a LARC method at 6 months (or no longer need contraception) then the primary effect measure for this outcome will be the intervention effect in non-LARC users. If conversely fewer than 90% of baseline LARC users in the control arm are using a LARC method at 6 months then the primary effect measure will be the overall adjusted intervention effect. A further subgroup analysis will be conducted for both primary outcomes to assess, based on testing an interaction term, whether the effect of the intervention varies by setting.

Primary comparisons between arms will be based on multiple imputation where outcomes at 6 months are imputed based on outcomes at 3 months for those participants who completed the 3 month outcome questionnaire but failed to complete the questionnaire at 6 months.

Health Economics

The primary analysis will be a budget impact analysis of the website and contraception reporting the total costs to each payer (NHS (primary care versus secondary care), local government, private and out of pocket). This will reported as total cost of contraception and pregnancy outcomes for a range of different population sizes. The analysis will conform to the ISPOR good practice guidelines for budget impact analysis.²¹

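### The booking route is likely to enrol women who have already decided on a LARC fitting; counted as baseline non-users and not identifiable from the described baseline items, they weaken the non-user contrast

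*Protocol*

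**What the plan says.** Section 4 (Summary) says that women requesting an appointment for "contraception will be invited to go online and enter the trial before they attend their appointment". Section 10.3 (Procedure) repeats the invitation on the Trust website and adds that "women who have booked a contraceptive appointment will be sent an additional text informing them that the clinic is taking part in a study". None of these places limits the invitation by type of appointment.

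Eligibility (section 10.1) covers "Women aged 15 to 30 years with a need for current or future contraception, attending one of the study sites". The exclusions are inability to consent and needing a language advocate. A method already chosen, or a fitting already booked, excludes no one.

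For baseline, section 10.4 describes a questionnaire on "what contraceptive methods, if any, they are using currently or have used before (baseline"), with satisfaction asked of current users. It mentions neither the intended method nor the reason for the appointment.

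Section 10.5 states: "The primary outcome of LARC use at 6 months will be analysed stratified by LARC use at baseline". If more than 90% of control-arm baseline LARC users are still on LARC at 6 months, or no longer need contraception, the effect in baseline non-users becomes the primary effect measure.

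Section 6 (Introduction) says that many general practices "have little or no capacity for fitting and therefore rely on referral to specialist contraceptive services".

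**The concern.** The booking site is the trial's specialist sexual and reproductive health service, the kind of service to which general practices refer women for fitting. With an unrestricted invitation, some women who enter before their appointment will probably have settled on a LARC method already. Under the plan they are eligible and not on LARC, so they are non-users. Most would be expected to be using LARC at 6 months in either arm, which leaves the website little room to raise their uptake.

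The 90% rule shows that the protocol recognises this problem for women already on LARC. It has no counterpart for women who have decided but not yet been fitted, and when it operates it moves the primary inference into the stratum that contains them. At stake are the size of the contrast in that stratum, its precision, and whether a small effect can be read as a weak website or as a population with little left to decide.

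**Working it through.** **The plan's own figure.** Section 9 states 82% power for 35% versus 47% with 930 women and 70% follow-up. Then n = 930 × 0.70 / 2 = 325.5 per arm (1:1 and two-sided 5% assumed), and

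power = Φ{[0.12 × √325.5 − 1.96 × √(2 × 0.41 × 0.59)] / √(0.35 × 0.65 + 0.47 × 0.53)} = Φ{(2.165 − 1.363) / 0.690} = Φ(1.161) = 87.7%.

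So 82% is not reproduced and is the more cautious figure. That is a separate matter and does not bear on this point.

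**Inputs for the illustration.**
- From the protocol: 651 analysed (930 × 0.70); booking-route share 530/930 = 57%; 24% LARC users at baseline (section 6, under-30s in specialist community services).
- Assumed: 90% LARC use at 6 months in both arms among baseline users and among decided women; 10% or 15% uptake in undecided control women, and 12 points more with the website; a share f of booking-route non-users already decided; the same route mix among non-users as overall.

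**Dilution in the non-user stratum.** The decided share of all non-users is q = f × 530/930. Control uptake is 0.90q + (1 − q)u, where u is uptake in undecided control women, and the contrast is 12 × (1 − q) points.

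| f | q | Control non-user uptake (u = 10% / 15%) | Contrast |
|---|---|---|---|
| 0 | 0 | 10.0% / 15.0% | 12.0 |
| 10% | 5.7% | 14.6% / 19.3% | 11.3 |
| 20% | 11.4% | 19.1% / 23.5% | 10.6 |

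The contrast shrinks modestly. Much of the loss comes from the extra variance due to a strong predictor of outcome that is missing from the model.

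**Power.** Logistic regression, two-sided 5%, 10,000 simulated trials per cell (simulation standard error at most 0.5 points); each cell gives u = 10% / 15%.

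| f | Arm + baseline LARC | Plus already decided | Non-users only | Undecided non-users only |
|---|---|---|---|---|
| 0 | 92% / 86% | – | 96% / 91% | 96% / 91% |
| 10% | 83% / 77% | 88% / 83% | 88% / 83% | 95% / 89% |
| 20% | 72% / 67% | 85% / 78% | 79% / 73% | 93% / 87% |

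A separate set of simulated trials under the same assumptions gave 92%/86%, 82%/78% and 72%/71% for the first column of results and 87%/83% and 83%/80% for the second. The two sets agree to within four points.

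**If the planned contrast already includes decided women.** Hold the overall rates at 35% and 47%. The effect needed in undecided women is then 12 / [0.76 × (1 − q)] points: 15.8 at q = 0 and 17.8 at q = 11.4%. Power adjusting for baseline LARC only stays at 96% to 97% across this range, and the extra covariate raises it to 98% to 99%. On this reading almost nothing is lost overall.

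**The case against.** The strongest reply has five parts.

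- **The baseline form is not shown.** Section 10.4 is a summary: section 10.6 mentions three quality-of-life questions that it does not list. A question on appointment purpose may exist. This stands, and the fix is conditional on it.
- **The presence of such women is inferred.** No passage says that fitting appointments are made through this route, and the remark about general practices is background. This also stands. The inference is reasonable but gives no share.
- **The power loss depends on the assumptions.** Section 9 powers an overall contrast, which may already include decided women. A reader might infer that the trial is underpowered as designed; the documents do not support that, as the last calculation shows. Nor should f be applied to all 930 women when the concern centres on the 530.
- **The website may still matter to decided women.** The outcome is use at 6 months, the aim includes adherence, and the content addresses side effects and concerns. To say that the website cannot raise LARC use in them goes too far; little room is as much as can be said.
- **The effect among all attenders is a legitimate pragmatic target, and covariates belong in the analysis plan.** The first half stands, so the overall effect should be kept. The second answers only part: an analysis plan can add a covariate only if it was collected, and asking after randomisation risks an answer shaped by allocation.

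A reader might also infer bias between arms. There is none, since randomisation balances decided women. Women booked for a removal are baseline users and already have their own stratum.

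**Conclusion.** The point holds as a limited design weakness. On the protocol's description, women already decided on a LARC fitting can enter, would be classed as non-users, and could not be separated later. The consequence is lost contrast and precision and a non-user effect that is harder to interpret.

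The size is unknown because the share is not documented. Under the assumptions above, 10% to 20% decided women among booking-route non-users costs roughly 8 to 20 points of power in the model adjusted for baseline LARC alone, and the covariate recovers about half or more of that. If 35% versus 47% already allows for such women, the gain is mainly in interpretation. Waiting-room recruitment has the same gap, but the booking route supplies most of the sample and was added to power this outcome.

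**What to change.** Unless the baseline form already asks it, add one question before randomisation, on both recruitment routes: has the woman already decided on, or is this appointment for, having a LARC method fitted, given, replaced or removed, and which? Prespecify the answer as a covariate beside baseline LARC use in the primary LARC model. Report the effect in undecided baseline non-users as a secondary, supporting estimate, leaving the primary effect measure as the protocol defines it. Report the share of decided women by route, which the definitive trial's sample size will need.

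Eligibility and care do not change. The cost is one more item in a questionnaire that section 10.3 says was deliberately shortened because participants in the team's earlier online trials found enrolment and baseline questions burdensome. The item must be in place before enrolment, since a reliable pre-randomisation answer cannot be obtained afterwards.

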5. TRIAL FLOW CHART

Framework of the trial software: online study information, consent, registration, data collection and randomisation

6. INTRODUCTION

Control of fertility is crucial to the health and wellbeing of women, but unintended pregnancy remains common and costly for both health services and individuals. In the UK, despite a range of freely available effective contraceptive methods, abortion rates have changed little over two decades (at around 190,000 per year for women resident in England & Wales). Despite a national teenage pregnancy strategy and recent fall in under-18 conceptions, England still has the highest rate of teenage pregnancy in Western Europe. A key report on the economics of sexual health concluded that it should be feasible to improve contraception and abortion services in ways that better meet the preferences of service users and that this could lead to a net saving of up to £1 billion over 15 years (1). In addition to the economic burden of unintended pregnancy and abortion to the NHS, and the emotional burden to individual women, unintended pregnancy plays a prominent role in persistent health inequalities in the UK and globally.

Preventing unintended pregnancy involves many steps, including timely education, awareness and socially patterned behaviours that lead women to seek, choose and use contraception consistently and correctly. Health services have a key role in supporting women to choose and use an appropriate method that best meets their needs. However, many women are still not aware of the range of different methods available to them. There are widespread myths about contraception, e.g. fears about impact on future fertility, weight gain or the significance of amenorrhoea. The pill and condoms are well known and widely used - by around half of all women on contraception - but they are not the most effective contraceptive methods.

Long-acting reversible contraceptive (LARC) methods, including intrauterine devices, depo injection and subdermal implants, offer women the most effective protection against pregnancy. Women who use oral contraceptive pills, the contraceptive patch, or vaginal ring have a 20 times higher failure rate than women who use LARC methods (2). Nearly a decade ago, NICE concluded that increasing uptake of LARC is more cost-effective in reducing unintended pregnancy than the contraceptive pill or condoms even at one year (3). At that time estimated uptake of LARC in the UK was low at 8% (2003/4 data) compared with 25% for the pill and 23% for male condoms. Since then, uptake of LARC has increased, but only slowly to 12% in the population in 2008/9 and to 30% by 2013 in women attending community contraceptive clinics (4). Even in specialist community services, younger women are less likely to use LARC (24% in those under 30 years) than older women.

There are **multiple pathways** by which women get information about contraception and choose a method. The main sources of information are the internet, family and friends, school sex and relationships education (SRE), general practitioners, community pharmacies and sexual & reproductive health services. However, not all these sources provide information on LARC and uptake of LARC is limited by the number of appropriately trained

doctors or nurses to fit them: many general practices - where 75% to 80% of contraceptive consultations occur - have little or no capacity for fitting and therefore rely on referral to specialist contraceptive services. The emergency intrauterine device (IUD) is much more effective than the emergency pill, but uptake of the emergency IUD remains low and community pharmacies - the first destination for the majority of young women seeking emergency contraception - cannot provide the emergency IUD. Recent surveys show that women's knowledge and experience of post-natal contraception is often poor (Sex and contraception after childbirth. British Pregnancy Advisory Service July 2014). Effective interventions are needed that expand women's choice of more effective methods of contraception, and improve uptake in a variety of settings.

Current **standard care pathways** for contraception vary considerably within and between different settings. Some services provide leaflets (e.g. the Family Planning Association, FPA) explaining the different methods, but the extent to which such leaflets are read, understood or help women reach an informed decision about contraceptive method is unclear. The quality of face-to-face consultation varies widely between different health care providers with different skills, competencies and experience. The evidence base for improving contraceptive uptake and adherence through better face-to-face consultation-based study of why women stop or switch contraceptive methods concluded that traditional consultation with a doctor or nurse in clinic has only modest influence on women's contraceptive decisions.

Health care in the UK is undergoing a **health informatics revolution**. The vast majority of young people have access to digital technology through Internet or mobile phones, which offers huge potential for health promotion. Recent data from the Office of National Statistics (ONS) indicate that 99% of 16-24 year olds have accessed the internet and 88% use it daily (8). We know that younger women are likely to turn to digital resources for information on contraception (9). For the proposed study, we will therefore explore the use of a website that provides information and decision support for contraceptive choices (10-13). The website will be available directly to users for self-guided use, and may be delivered by any digital media, including the internet, mobile telephone, and handheld computers. Access can be private and self-paced, and programmes can be tailored according to individual preferences. Digital interventions are effective at increasing knowledge of emergency contraception (14) and there is evidence of effect on sexual behaviour, (10) contraceptive choice and adherence (11-13). However, we are not aware of any services in the UK that currently provide interactive digital interventions to support women's contraceptive decision making. Our intervention development field-work has confirmed that women and health providers support the idea of a website for contraception choice, to be offered in clinic settings.

The proposed research is timely because it aims to provide women with better information and support to make informed choices about contraception that may have long-lasting effects on their health and wellbeing. Evaluating interventions that can be implemented within busy settings proving contraception services to improve informed choice, access, uptake and adherence to effective contraceptive methods, including LARC, which is a key priority for the prevention of unintended pregnancy in the UK.

In Phase 1 of this study a **systematic review** was undertaken to review evidence on individual level education or decision aid interventions relating to acceptability, uptake and adherence to contraception, including underpinning theories and user and provider views. In addition, we conducted a qualitative evaluation of women's views of contraception, with a focus on contraceptive myths and misconceptions on social media sources such as Youtube and various online forums.

Health professionals from each of the five study settings (GP practice, sexual health clinic, maternity ward, abortion service, and community pharmacy) were interviewed using a semi-structured interview, to gather information on their views of women's contraceptive knowledge and needs, and the perceived challenges to supporting and understanding contraceptive decision-making, to hear their experiences of existing websites (if any) and their preferences for future websites as well as to understand how a website can complement, enhance or replace and/or fit with established services. In addition, an **expert workshop** was facilitated in order to gain insight on intervention content from a wider range of professionals, including experts in e-health, psychology, decision aids and human-computer interaction.

Women aged 15 to 30 were invited to either focus groups or individual interviews to gather insight into their contraceptive beliefs, experiences, when, where, why and how they access information on contraceptives, and how they make personal choices and decisions around contraception.

Findings from the social media evaluation, qualitative interviews with health professionals as well as focus groups and interviews with women from each of the five study sites were in line with each other, so sampling stopped once data saturation had been reached.

Our main findings were that:

-Women don't fully understand contraceptive side-effects

-There tends to be an underestimation of contraceptive benefits and an overestimation of contraceptive side-effects

-The 'unnaturalness' of hormones is by far the most common concern

-Infertility, irregular bleeding, no periods, and cancer are side-effects women are also particularly worried about

-Partners' views are important to women

-Many women think it is unhealthy to skip periods

-Many women think their bodies need a break from contraception

-Women like seeing honest videos of other women talking about their experiences of contraception

-Women don't like seeing too much text on a website and would prefer to have options for more information if they wish to know more

The intervention website

We have integrated the findings from the systematic review, women's views on social media, the expert workshop, and interviews with women and health professionals, to develop a trial-ready self-guided website that presents a number of contraceptive options in response to input of women's preferences and concerns. The website will be ready for launch in January 2017.

